Of the eight published trials of tDCS to date, three have directly targeted fatigue. As shown in **Table 1**, all three have used sham-controlled crossover designs, and found significant improvement in fatigue following active treatment in either the full group or subset analyses. Each of the three studies varied in their montage with similar results.

Table 1 . tDCS studies of fatigue in MS to date, including our feasibility study and proposed study							
Author (Year)	Sample n	Design	#Sessions, Treatment Montage				
Ferrucci et al. (2014) 	25	Sham-controlled crossover	5 sessions x 1.5 mA motor cortex x 15 minutes				
Saiote et al. (2014 ) 	13	Sham-controlled crossover	5 sessions x 1.0 mA DLPC x 20 minutes				
Tecchio et al. (2014) 	10	Sham-controlled crossover	5 sessions x 1.5 mA x 15 minutes; sensorimotor cortex				
Protocol feasibility study	17	Open-label (remote protocol)	10 sessions x 1.5 mA DLPFC x 20 minutes				

Two of the three studies included analyses to link to the mechanism of benefit, with unclear results. Saiote et al. included MRI and found a correlation between lesion load in left frontal cortex and reduced fatigue following tDCS treatment. In a follow-up second analyses, Tecchio et al. found tDCS treatment was more effective against MS fatigue when the electrode was focused on the bilateral whole body somatosensory area (but changes in S1 and M1 excitability did not correspond to treatment benefit).

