# IV. SPECIFIC AIMS

Specific Aim 1: To test the feasibility of a randomized, controlled remotely-supervised tDCS clinical trial protocol developed specifically for use in MS. Participants (n=85) will be randomly assigned to receive 40 x 20-minute sessions of either active (up to 2.5 mA) paired with cognitive remediation, to two separate control conditions. The first is an active tDCS condition paired with non-adaptive, traditional puzzle and board games and will act as this study's negative control. The second control will act as the study's positive control and will be sham tDCS paired with cognitive remediation. Each study session, regardless of study arm, will be followed by an additional 10 minute computerized training sessions post-stimulation. Each study arm will complete 40 sessions over eight weeks.

The *primary outcome* for feasibility will be the number of participants completing at least 80% or n=32of the targeted 40 sessions. Secondary outcomes will be comparison of tolerability and participant- reported side effects between the two treatment arms.

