# e)Analytic Plan:

Specific Aim 1 is to determine feasibility; to be measured by the number of participants successfully completed using the proposed protocol for training and monitored administration. As would be expected, there is a high rate of compliance for in-clinic tDCS administration and therefore remotely-supervised administration should be designed to be similarly compliant. Study success will be defined by 80% participants having completed 80% sessions, shown to be the target compliance for previous tDCS studies. We will also determine the effectiveness of our sham procedures to ensure blinding, as tested by comparing those who accurately identified the sham condition. We will assess whether the frequency or type of side effects differ between the active and control conditions and whether they occur at the same rate as reported from studies of in-clinic administration. Secondary outcomes will be tolerability, participant-reported adverse events, and comparisons of active and control conditions on these measures.

Specific Aim 2 will be to determine preliminary signals for efficacy, and to have pilot findings to determine necessary sample sizes for an adequately-powered clinical trial. For each participant, change scores will be calculated between baseline and study end scores on measures of fatigue and cognitive functioning. These difference scores will then be described and compared between groups (t-tests and ANOVA related analyses) to determine signals of efficacy for active tDCS paired with cognitive remediation vs. active tDCS paired with non-adaptive puzzle and board games vs. sham tDCS paired with cognitive remediation.

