# **Statistical Analyses**

Analyses will be completed with IBM SPSS v. 23. Means, medians, standard deviations (SD) will be compared between subgroups on the measures using conventional cut-off points for each of the symptoms will be compared.

Specific Aim 1 will be tested by comparing the number of participants in each condition meeting the study definition of compliance (having completed 80% sessions). We will also determine the effectiveness of our sham procedures to ensure blinding, as tested by comparing those who accurately identified the sham condition. We will assess whether the frequency or type of side effects differ between the three conditions and whether they occur at the same rate as reported from studies of inclinic administration.

Specific Aim 2 will be to determine preliminary signals for efficacy, and to have pilot findings to determine necessary sample sizes for an adequately-powered clinical trial. For each participant, change scores will be calculated between baseline and study end scores on measures of fatigue and cognitive functioning. These difference scores will then be described and compared between groups (t-tests and ANOVA related analyses) to determine signals of efficacy.

Cognitive performance will be evaluated for those who completed at least 18 sessions. We conservatively plan for comparison of 15 participants in each group, allowing for up to 33% dropout. While both cognitive remediation groups are expected to improve with cognitive training, we hypothesize that the active tDCS condition will gain one standard deviation (of the published normative mean) or more in score than the sham condition and that the group with active tDCS paired with non-adaptive puzzle and board games will neither improve nor decline.

Secondary outcomes will be used to compare the groups in change in performance on the additional measures listed in Table 2. These are the most commonly-used outcome measures in MS trials

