The safety of this technique has been addressed and tested by multiple researchers (e.g., Hummel, et al.; Fregni, et. al.; Nitsche, et al.; Priori, et al.) who have concluded that tDCS, as applied in a manner similar to our proposed protocol, induces only temporary mood, cognitive / motor effects, and no negative side effects. For example, researchers at the National Institute of Neurological Disorders and Stroke (NINDS), Iver et al. conducted a safety study on tDCS, investigating 20-minute sessions of 1 mA and 2 mA current stimulation with healthy controls (n=103). No negative effects were identified. Nitsche and colleagues found no measurable structural changes in brain tissue due to tDCS. In a meta-analysis of over 200 tDCS studies conducted from 1998 to 2010, 56% of studies mentioned adverse events, which were generally minor. The most commonly reported side effects included itching, tingling, headache, burning sensation and discomfort limited to the scalp site where the tDCS electrodes were applied. To date, there have been no reports of seizures induced by tDCS. Importantly this is the case in normal volunteers, but also in different populations of patients, including patients with disorders where there might be an increased risk of seizures (e.g. Alzheimer's disease, recent stroke, epilepsy). A study from NYU on the use of tDCS in patients with epilepsy encountered no increase in complications of tDCS in the patients as compared with controls. Specifically, there were no instances of seizures induced by tDCS.

Participants in all groups may find the questionnaires time consuming and potentially bothersome. Neuropsychological testing and the computer training sessions may, in some individuals, be stressful or anxiety producing. There is a small risk of loss of confidentiality. Participants will be assigned a study ID and their name will not be used on any of the information collected. The program used for brain training games will not collect any personally identifiable information. The results of these data collected may be used for publication but will not include the participants' names. Hardcopies of the data files will be kept in secure, locked files and data will be entered in a secure, NYU approved database

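### The Aim 1 comparison of side-effect rates with published in-clinic studies is historical and has no named comparators, so neither a match nor a difference can be attributed to home delivery

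*Combined protocol and SAP*

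**What the plan says.** The comparison is written twice. Section V.e (Analytic Plan, Specific Aim 1) says the team will assess "whether they occur at the same rate as reported from studies of in-clinic administration", and section IX (Statistical Analyses, Specific Aim 1) repeats it almost word for word: "whether they occur at the same rate as reported from studies of inclinic administration". Neither place names the reference studies, a reference rate, the unit (session or participant), a margin or a test. The same sentence in each place also plans a comparison of side effects across the study conditions.

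Side effects are not what decides Aim 1. Section V.e states: "Study success will be defined by 80% participants having completed 80% sessions". Its secondary outcomes "will be tolerability, participant-reported adverse events, and comparisons of active and control conditions on these measures".

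On exposure, section IV plans "40 x 20-minute sessions of either active (up to 2.5 mA" at target), and section V.a allows reduction to 2.0, 1.5 or 1.0 mA after tolerability testing. Section VI places sessions 2 to 40 in the home for all participants. Table 1 describes the first published MS fatigue study as "5 sessions x 1.5 mA motor cortex x 15 minutes"; the other two also used 5 sessions, at 1.0 and 1.5 mA. On recording, the Risk to Participants section reports that in a review of more than 200 tDCS studies "56% of studies mentioned adverse events, which were generally minor".

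**The concern.** The sentence reads as a check on whether remote delivery is as well tolerated as delivery in clinic. No MS arm is treated in clinic beyond the first session, so the only reference is other people's published results. Those results may differ from this trial in how many sessions were given, at what current, and how actively side effects were sought.

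A higher rate here could come from more sessions, higher current or fuller recording, and a similar rate could hide a real effect of setting. This trial asks about tolerability by staff interview and by self-report before and after each session (Table 2), and section IX (Monitoring) counts side effects or sensations arising around stimulation as adverse events. That is a wide net next to a literature in which many reports do not mention adverse events. The stake is an Aim 1 statement on equivalence to in-clinic treatment that could be carried into the design of later trials without support. Because the comparators are unnamed, they could also be chosen after the trial's own rates are known.

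**Working it through.** The plan gives no reference rate, margin or power for this comparison, so there is no figure of its own to reproduce. The check has two parts.

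**1. How the described in-clinic studies differ from this trial**

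| Feature | Studies described in the protocol | This trial |
|---|---|---|
| Sessions | 5 in each of the three published MS fatigue studies (Table 1); 20 to 30 or more for some depression patients (section II) | 40 |
| Current | 1.0 to 1.5 mA (Table 1); 1 and 2 mA in a safety study of healthy controls (Risk to Participants) | up to 2.5 mA, with 2.0, 1.5 or 1.0 mA possible |
| Recording | adverse events mentioned in 56% of more than 200 studies, 1998 to 2010 | solicited before and after every session |

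Table 1 marks only the feasibility study as remote, so I take its three published studies as in-clinic.

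**2. What session count alone can do if the unit is the participant**

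Assumption: a per-session risk p = 5%, the same at home and in clinic. The documents give no such rate.

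- Independent sessions: P(any event in k sessions) = 1 − (1 − p)^k.
  - k = 5: 1 − 0.95^5 = 0.226
  - k = 40: 1 − 0.95^40 = 0.871
- Within-person correlation ρ = 0.3 (assumed), beta-binomial: a = p(1 − ρ)/ρ = 0.05 × 0.7/0.3 = 0.117 and b = (1 − p)(1 − ρ)/ρ = 0.95 × 0.7/0.3 = 2.217. P(any event) = 1 − ∏ (b + i)/(a + b + i) for i = 0 to k − 1.
  - k = 5: 0.144
  - k = 40: 0.307

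The same formulas show how the gap depends on the assumptions:

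| p | Correlation | 5 sessions | 20 sessions | 30 sessions | 40 sessions |
|---|---|---|---|---|---|
| 1% | 0 | 4.9% | 18.2% | 26.0% | 33.1% |
| 2% | 0 | 9.6% | 33.2% | 45.5% | 55.4% |
| 5% | 0 | 22.6% | 64.2% | 78.5% | 87.1% |
| 5% | 0.3 | 14.4% | 25.3% | 28.5% | 30.7% |

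The gap is wide against a 5-session reference. It narrows against a 20- or 30-session reference and when events cluster in the same people. With the session as the unit the expected rate is p in both settings, so this artefact disappears. Differences in current and recording remain.

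**The case against.** The other side has several good points.

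- **Aim 1 does not rest on this.** A reader might infer that home delivery will be judged by the in-clinic comparison. The documents do not support that: the success rule is session completion, side effects are secondary, and the in-clinic clause carries no decision rule. The study is a pilot. The same sentence also plans a comparison across randomised arms that share setting, schedule and recording. All of this stands, and it limits the weight of the point.
- **The comparators are unknown.** It is tempting to say that the in-clinic studies used fewer sessions, lower currents and poorer reporting throughout. Table 1 lists fatigue studies and is not offered as the side-effect reference. Longer depression courses and 2 mA stimulation are described, and trial participants on reduced current overlap with published currents. The 56% figure covers tDCS studies generally, and a study silent on adverse events would simply supply no rate. This also stands, but an open choice of comparator does not remove the confounding.
- **Exposure ratios are not bias.** At target the trial delivers 40 × 20 × 2.5 = 2000 mA-min, against 5 × 20 × 1.0 = 100 to 5 × 15 × 1.5 = 112.5 in Table 1, or 18 to 20 times. Nothing in the documents ties side-effect rates to cumulative current, so this ratio does not measure the error.
- **The team may report per session.** Figure 1 presents its earlier experience that way. That would remove the session-count artefact, but the plan does not commit to it.

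What survives is that, whichever studies and unit are chosen, setting is not the only thing that differs.

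**Conclusion.** The point holds as a limited one. The planned comparison cannot show that home delivery has the same side-effect rate as in-clinic delivery, or a different one, because setting cannot be separated from session count, current and recording. This rests on the plan's own description and needs no assumed rate.

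The size of the session-count artefact does rest on assumptions. With a per-participant unit, a 5-session reference and a 5% per-session risk, it runs from 14% against 31% (correlation 0.3) to 23% against 87% (independent sessions). With a per-session unit it is zero. The documents give no basis for sizing the effects of current or recording.

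The primary outcome, the success rule and the randomised comparison of side effects are untouched.

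**What to change.** In sections V.e and IX, Specific Aim 1:

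1. Name the in-clinic reference studies before the data are analysed, limited to those that solicited side effects at each session.
2. Compare per-session rates within current level, with confidence intervals that allow for repeated sessions per person.
3. State that this comparison is descriptive and does not test the effect of home delivery, and that the randomised between-arm comparison is the inferential side-effect analysis.

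Do not substitute session 1 (baseline visit) against sessions 2 to 5 (home) as the test of setting. Session 1 is always the first exposure and the training session, so setting is confounded with order. Subtracting the sham change would remove any home effect shared by the arms and would leave habituation to sustained current. It would also be imprecise. Assume a 5% rate, correlation 0.3, 57 participants on active current and 28 on sham (85 split 1:1:1, no dropout). The variance of a within-person difference is 0.0475 × [1 + (1 + 3 × 0.3)/4 − 2 × 0.3] = 0.0416. The standard error is √(0.0416 × (1/57 + 1/28)) = 0.047, a 95% half-width of about 9 points around a 5% rate.

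The cost is wording and a literature selection made in advance, with no new data. The downside is fewer usable reference studies and no claim of equality with in-clinic rates.

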**c)** Randomization: Participants will be assigned to each condition in a 1:1:1 Stratified randomization procedure. Participants will be matched according to the degree of cognitive impairment (Symbol Digit Modalities test or SDMT score) and neurologic (motor) impairment (Expanded Disability Status Scale or EDSS score). Participants will be randomized to either the active tDCS condition paired with cognitive remediation or one of the two control conditions. The positive control condition will consist of cognitive remediation paired with sham tDCS and the negative control condition will consist of active tDCS with non-adaptive puzzle and board games using block randomization of permuted block sizes 3 and 6, based on our experience in cognitive remediation trials. SDMT performance will be categorized compared to published age-normative means (>0.99 SD, 1 to 2 SD and 2 to 3 SD below mean) and EDSS score will be categorized as mildly or moderately impaired (0 to 3.0 vs. 3.5 to 8.0).

d)*Outcome Measures:* Before and after each session, participants will complete brief measures to monitor for any stimulation-related events as well as mood and fatigue. In addition a pain scale will be administered during the session. Participants will also complete baseline and study-end inventories of mood and fatigue and complete a brief battery of cognitive tests including the Brief International Assessment of Cognition in MS or BICAMS, to help guide power estimates for the future trials. A summary of outcome measures can be found in Table 2.

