# **Table 2. Study Outcome Measures**

Test	Screen ing	Baseline	Daily Study Session s (1-20)	Mid- study	Daily Study Sessions (21-40)	Study End (Follow- up)	Online/ Telephone Survey (Study end date + 1 month)
Medical Clearance	Х						
Expanded Disability Status Scale	X						
Wide Range Achievement Test (WRAT-4)	X	X				X	
Symbol Digit Modalities Test (SDMT)	X	X		X		X	
Beck Depression Inventory-Fast Screen*		Х				X	
tDCS Aptitude Test		X				Х	
tDCS Tolerance Test (2.0 mA, will possibility to repeat at 1.5 mA)		X				Х	
Multiple Sclerosis Neuropsychological Questionnaire (MSNQ)*		Х		X		Х	X
PROMIS Measure of Fatigue, Mood and Health- Related Quality of Life*		X		Х		Х	X
Neuro-Quality of Life*		X		Х		X	X
Fatigue Impact Scale*		Х		Х		X	Х
Fatigue Severity Scale*		Х		Х		X	Х
Pittsburgh Fatigability Scale*		Х		X		X	
Attention Network Test- Interaction*		Х		X		X	
Cogstate Brief Battery*		Х		Х		Х	
ERTSLab Processing Battery*		Х		X		Х	
Controlled Oral Word Association*		X		Х		Х	
Rey Auditory Verbal Learning Test*		X		X		X	X (delayed recall only)
Brief Visuospatial Memory Test- Revised*		Х		Х		Х	
King Devick Test*		Χ		Χ		Х	
Test of Everyday Cognitive Ability*		X		X		X	
Grip Strength*		Х		Х		Х	
Grooved Pegboard*		Х		Х		Х	
Positive and Negative Affect Scale (PANAS)*		Х	Х	Х	Х	Х	
Visual analog scale for		Х	X	Х	X	X	

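### Aim 2 compares change scores between arms with no stated adjustment for the baseline score; naming a baseline-adjusted model would usually give slightly better precision from the same data.

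*Combined protocol and SAP*

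**What the plan says.** Section V(e), Analytic Plan, defines the Aim 2 endpoint: "For each participant, change scores will be calculated between baseline and study end scores on measures of fatigue and cognitive functioning". Section IX, Statistical Analyses, repeats this and gives the test: "These difference scores will then be described and compared between groups (t-tests and ANOVA related analyses) to determine signals of efficacy". Neither section names a covariate. Section IX carries a similar analysis over to the secondary outcomes and examines clinical features only by correlation. The reference list includes a paper comparing baseline-adjustment methods (item 111), but I found no citation of it in the body text.

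One stated purpose of Aim 2 is "to have pilot findings to determine necessary sample sizes for an adequately-powered clinical trial". For cognition, Section IX says: "We conservatively plan for comparison of 15 participants in each group, allowing for up to 33% dropout". It also expects that the games arm "will neither improve nor decline".

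Section V(c) stratifies randomisation: "Participants will be matched according to the degree of cognitive impairment" on the SDMT, and also on EDSS category. Fatigue is not a stratification factor. Table 2 collects the fatigue and cognitive measures, for example the "Fatigue Severity Scale", at both baseline and study end.

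**The concern.** Comparing raw change scores amounts to assuming that each extra point at baseline carries through as exactly one extra point at study end. When the true slope differs from 1, part of any chance baseline difference between arms stays in the contrast as noise. Fatigue is not balanced by design, and as few as 15 per group may be analysed for cognition, so such differences will occur. A model that estimates the slope removes this noise and needs no further data.

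The stakes are the width of the intervals from which efficacy signals are read, and which variance is carried into the design of the next trial. The ANOVA-type wording could include analysis of covariance, so the model is also left open across many measures.

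**Working it through.** **Inputs.** 85 MS participants in three arms, 1:1:1 (Sections V and VII). 15 per group for cognition (Section IX). The baseline-to-study-end correlation r is not given; I assume 0.5, 0.7, 0.8 and 0.9. The ratio k of study-end SD to baseline SD is not given; I take k = 1 first, then vary it.

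**The plan's own figure.** 85/3 = 28.3 per arm, and 28.3 × 0.67 = 19.0, not 15. Fifteen per group is 45 of 85, a loss of 1 − 45/85 = 47%. The stated 15 therefore does not follow from 85 and 33% dropout. That is a separate matter; here I use 15 per group and all 85 as the two ends of the range.

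**Equal SDs (k = 1).** With common SD s:
- Var(change) = 2s²(1 − r)
- Var(baseline-adjusted) = s²(1 − r²)
- ratio = (1 + r)/2

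Estimating the slope multiplies the adjusted variance by about 1 + 1/(N − 5): 1.025 at N = 45 and 1.0125 at N = 85. The lost degree of freedom (42 to 41 at 15 per group) adds under 0.1% to the width. The relative interval width is the square root of the product:

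| r | (1 + r)/2 | 15 per group | all 85 |
|---|---|---|---|
| 0.5 | 0.75 | 0.877 | 0.871 |
| 0.7 | 0.85 | 0.933 | 0.928 |
| 0.8 | 0.90 | 0.960 | 0.955 |
| 0.9 | 0.95 | 0.987 | 0.981 |

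The intervals are thus about 12%, 7%, 4% and 1% narrower at 15 per group, and 13%, 7%, 5% and 2% narrower with all 85. Three-arm simulations agree. An unstratified run at 15 and 28 per arm (8,000 runs per setting) gave type I error of 0.046 to 0.054 for both methods and no bias in either.

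**Unequal SDs.** In general the variance ratio is (1 − r²)k² / (1 + k² − 2rk). For r = 0.8 and k = 1.1 this is 0.36 × 1.21 / (1 + 1.21 − 1.76) = 0.4356/0.45 = 0.968, and √(0.968 × 1.025) = 0.996. Relative widths at 15 per group:

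| r | k = 0.8 | k = 1.0 | k = 1.1 | k = 1.2 |
|---|---|---|---|---|
| 0.7 | 0.80 | 0.93 | 0.97 | 1.00 |
| 0.8 | 0.81 | 0.96 | 1.00 | 1.01 |
| 0.9 | 0.79 | 0.99 | 1.01 | 1.00 |

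The denominator exceeds the numerator by (1 − rk)², so the ratio never passes 1. The only cost is estimating the slope: √1.025 = 1.012, or about 1% in width at 15 per group.

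**A rough guide to r.** Section III gives change SDs of 0.36 and 0.31 in the group's n=135 trial: pooled √((0.36² + 0.31²)/2) = 0.336. With r = 1 − SD²/(2s²) and an assumed baseline SD of 0.5 to 1.0, r is 0.77 to 0.94. The n=20 trial (0.59 and 0.48, pooled 0.538) gives 0.42 to 0.86. Both concern a composite that this protocol does not define as an outcome.

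**Adding the randomisation categories.** At 15 per group, baseline plus SDMT and EDSS categories gives simulated relative widths of about 0.90, 0.95, 0.98 and 1.01 at r = 0.5, 0.7, 0.8 and 0.9. That is about 2% wider than baseline alone when the categories predict nothing further.

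**Sizing the next trial.** Under equal SDs, a trial that will adjust for baseline but is sized from the change-score SD is too large by 2/(1 + r): 1.33, 1.18, 1.11 and 1.05.

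**The case against.** The strongest reply is that this is a preference, not an error. Aim 2 looks for preliminary signals in a pilot, its hypotheses are worded as gains, and a change score answers them directly. The existing wording may already cover analysis of covariance. If r for cognition lies in the 0.77-0.94 range suggested by the larger earlier trial, the gain at 15 per group is only about 5% to nil under equal SDs. Nor has the plan yet chosen a single Aim 2 measure. All of this stands, and it is why the point is minor.

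A reader might go further than the documents allow in three ways:
- **That adjustment can never lose.** It can, by about 1% in width, when the study-end SD is 10-20% above baseline and r is 0.8-0.9.
- **That the stratification factors should be added for precision.** At 15 per group they cost about 2% unless they predict the outcome beyond baseline. Section III itself says that fatigue is not consistently linked to EDSS.
- **That the next trial will be oversized.** This requires a later design that adjusts for baseline yet uses the unadjusted change SD. No section says so, and r and the residual SD could still be calculated from the stored data.

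What survives is that no section states a baseline adjustment, and that adding one usually helps and costs almost nothing.

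**Conclusion.** The point holds as a minor matter of efficiency and pre-specification. It would be wrong to infer that the planned analysis is biased or invalid: under randomisation it is neither.

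The size depends on two quantities that the documents do not give. With equal SDs the gain in interval width at 15 per group runs from about 12% at r = 0.5 to about 1% at r = 0.9. It is about 20% if the study-end SD is 0.8 of baseline. It is nil, or a loss of about 1%, if the study-end SD is 10-20% larger and r is 0.8-0.9. Only adjustment for the baseline score is supported as the core change. The effect on the next trial's size is conditional.

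**What to change.** In Sections V(e) and IX, make the between-arm Aim 2 analysis a linear model (ANCOVA) of the study-end score on arm (three levels) and the baseline score of the same measure. Report 95% confidence intervals for active tDCS with training versus sham with training, and for active tDCS with training versus active tDCS with games. Report the residual SD and the observed baseline-to-study-end correlation for sizing the next trial. Keep change scores as description, including for the within-arm expectation about the games arm. The SDMT and EDSS categories used at randomisation may be added as a sensitivity analysis, without claiming a gain in precision.

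The cost is a change of wording and one degree of freedom, with at most about 1% in interval width in the settings checked. The change score already needs both values, so the participants and data are the same. Where an optional Table 2 measure is not collected, neither analysis is possible.

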# **Specific Aim 2:** To test the preliminary efficacy of tDCS to treat fatigue and to enhance outcomes of cognitive training. These data will inform the design of a large, controlled clinical trial.

The *primary outcome* will be comparisons between the active and control conditions on measures of fatigue and cognitive functioning.

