# Figure 2. Study stop criteria

#### A "Stop" necessitates treatment discontinuation. A study end visit may be conducted after a "Stop" if necessary (i.e. midway through sessions).

#### Screening:

Participants for all groups will be recruited from the NYU Langone Medical Center Multiple Comprehensive Care Center. Once a potential participant is identified, a screening phone call will take place to determine general eligibility (See section IX. Consent Process). Once a participant is deemed generally eligible, the individual will be scheduled for a visit at NYU to review and sign consent and complete screening procedures, including a medical clearance. For those interested in study participation, once eligibility is confirmed by a NYU MS Center clinician, their baseline appointment will be scheduled.

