# **Study End Visit:**

Within three days of their last session (including same day), participants will have their final study end visit in clinic. The tests and evaluations administered at baseline will be given to the participant again (Table 1). The equipment that had been provided to the participant for this study will be returned on this visit.

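### The cognitive half of the Aim 2 primary outcome is analysed only in participants with at least 18 of 40 sessions, with no reason given; separately, 15 per group does not follow from n=85

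*Combined protocol and SAP*

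**What the plan says.** Section IV gives the Aim 2 primary outcome as one item with two parts: it "will be comparisons between the active and control conditions on measures of fatigue and cognitive functioning". The analysis is described in Section V.e and repeated in Section IX: "For each participant, change scores will be calculated between baseline and study end scores on measures of fatigue and cognitive functioning". These scores are then compared between groups by t-tests and ANOVA-type analyses.

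Section IX then adds, for cognition alone: "Cognitive performance will be evaluated for those who completed at least 18 sessions". Fatigue has no matching sentence. The next sentence reads: "We conservatively plan for comparison of 15 participants in each group, allowing for up to 33% dropout".

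The compliance threshold in Section IV is different. The primary outcome "for feasibility will be the number of participants completing at least 80% or n=32of the targeted 40 sessions".

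On who is assessed at the end, Section VI (Study End Visit) says: "Within three days of their last session (including same day), participants will have their final study end visit in clinic". It sets no minimum number of sessions. The note under Figure 2 (study stop criteria), in the same section, permits but does not require a study end visit after a stop, "if necessary (i.e. midway through sessions").

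**The concern.** The arms are comparable because of randomisation. Reaching session 18 happens afterwards and may depend on the assigned condition and on how the participant is doing. Restricting the comparison to those who reach it can make the arms differ for reasons other than treatment.

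The rule is also incompletely specified. The statement covering each participant may be the general rule and the 18-session sentence an exception for cognition, but the plan does not say so, and two analysts could build different cognitive data sets. Nothing explains why cognition needs a minimum exposure and fatigue does not, or why the minimum is 18. A minimum-exposure cut-off may legitimately differ from a compliance cut-off, so the gap is the missing reason, not the mismatch with 32.

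Aim 2 exists to provide estimates for sizing a later trial. A shift in the cognitive estimate would carry into that calculation, and the confidence interval would not show it.

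**Working it through.** **Thresholds.** 18/40 = 45% of sessions; the compliance rule is 32/40 = 80%.

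**Planned number per group.** Inputs: 85 randomly assigned (Section IV), 1:1:1 over three arms (Section V.c), dropout up to 33% and 15 per group (Section IX).
- Forward: 85/3 = 28.3 per arm; 28.3 × 0.67 = 19.0. The stated 15 is not reproduced.
- Backward: 15/0.67 = 22.4 per arm, and 3 × 22.4 is about 67 in total, not 85.
- Loss implied by 15 per arm: 1 − 45/85 = 47%.

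**Bias from the 18-session set.** The documents give no early-stopping rates by arm, so these are assumptions. Let q be the share of an arm stopping before session 18, z the normal quantile of q, φ the standard normal density, r the correlation between poor change and early stopping (0.3 to 0.5 assumed), and f the share of early stoppers with study-end scores, taken as a random sample of early stoppers. With no true effect, the bias between arms a and b, in SDs of change, is

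r × [φ(z_a)(1−f)/(1−q_a+f·q_a) − φ(z_b)(1−f)/(1−q_b+f·q_b)].

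The 18-session set corresponds to f = 0. For 33% versus 5%: φ(z) = 0.362 and 0.103, so the bracket is 0.362/0.67 − 0.103/0.95 = 0.432. Multiplying by r gives 0.130 (r = 0.3) and 0.216 (r = 0.5), in favour of the arm that loses more.

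| Early stopping, arm a vs arm b | r = 0.3 | r = 0.5 |
|---|---|---|
| 33% vs 33% | 0 | 0 |
| 6% vs 5% | 0.005 | 0.009 |
| 20% vs 5% | 0.072 | 0.121 |
| 33% vs 5% | 0.130 | 0.216 |
| 5% vs 33% | −0.130 | −0.216 |

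The 6% versus 5% row is in line with the earlier 10-session study: 95% completed at least 8 of 10 sessions (Section II), and compliance in the active condition was above 94% (Section IX, Monitoring).

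**Bias when all participants with study-end scores are included, 33% versus 5%.**

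| Share of early stoppers assessed (f) | r = 0.3 | r = 0.5 |
|---|---|---|
| 0 | 0.130 | 0.216 |
| 0.2 | 0.09 | 0.15 |
| 0.5 | 0.049 | 0.082 |
| 0.8 | 0.017 | 0.028 |
| 1 | 0 | 0 |

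A simulation of 20,000 trials with 28 per arm at r = 0.5 gave 0.218, 0.079, 0.026 and −0.001 at f = 0, 0.5, 0.8 and 1, in agreement with the formula.

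**Against sampling error.** The 95% CI half-width for a two-arm difference is t × √(2/n): 0.658 SD at n = 19 and 0.748 SD at n = 15. The largest illustrated bias is 0.216/0.658, about one third of the half-width.

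**Dilution from including early stoppers.** Section IX hypothesises a difference of at least 1 SD between active and sham. If a share q of each arm stops early, gains nothing and is fully assessed, 1 SD becomes 1 × (1−q): 0.95 at q = 5% and 0.67 at q = 33%. If only half of early stoppers are assessed, the 33% figure is 0.67/(0.67 + 0.5 × 0.33) = 0.67/0.835, about 0.80.

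**The case against.** The strongest reply is that this is a pilot looking for preliminary signals, with no stated alpha, and that the bias is negligible unless completion differs markedly between arms. No passage suggests that it will. This stands as a limit on the size of the problem. It does not supply a reason for the cut-off or for treating cognition differently from fatigue. The reassuring completion rates come from 10 open-label sessions, whereas this trial has 40 sessions in three arms and itself allows for up to 33% dropout.

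A second reply is that the remedy may achieve little. If few early stoppers return, the proposed set is nearly the 18-session set, and those assessed may not be typical of early stoppers. Including them may also dilute the estimate by as much as the bias removed. Under the stated model, low follow-up shrinks the gain but does not reverse it. The dilution is real, and it is the reason for keeping the 18-session set as a supportive analysis.

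Third, the Study End Visit paragraph already covers early stoppers on its face. The note under Figure 2 makes the visit discretionary after a stop, so the two still need reconciling.

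Fourth, 15 may be a deliberate floor, since the plan says it is conservative. Or 85 may count people who consent, some of whom are later excluded at aptitude or tolerability testing; about 67 randomised would then give 15 per arm at 33% loss. However, Section IV says that 85 will be randomly assigned, and the sentence in Section IX ties 15 to 33% dropout. The figures remain unreconciled as written.

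**Conclusion.** The concern holds. The plan applies an unexplained post-randomisation selection to one half of a joint primary outcome and leaves unclear how it relates to the rule covering each participant. It should be fixed, but its size should not be overstated. The bias is nil with equal loss and at most 0.01 SD at completion like that in the pilot. It reaches 0.13 to 0.22 SD only under an assumed 33% versus 5% split, and its sign depends on which arm loses more. The correlations, the losses by arm, the share of early stoppers assessed and the 95% level are assumptions, not figures from the documents.

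The planning figure is a separate and lesser point. About 19 per arm is expected at 33% loss; 15 understates this, shows no underpowering and adds nothing to the severity.

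**What to change.** Replace the 18-session sentence in Section IX with wording such as:

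*The main Aim 2 comparison, for both cognition and fatigue, will include all randomised participants with study-end scores, by assigned arm, whatever the number of sessions completed, using the planned change-score analysis (t-tests and ANOVA). Participants who completed at least 18 sessions will be reported as a supportive analysis only.*

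State the reason for 18. In Section VI, reconcile the note under Figure 2 with the Study End Visit paragraph so that study-end scores are sought from participants who stop early. This concerns outcome assessment only and leaves the stop criteria as they are. Restate the planning figure as about 28 randomised and about 19 evaluable per arm at 33% dropout, or say that 15 is a floor corresponding to about 47% loss.

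The cost is a few sentences and some additional study-end visits, plus the possible dilution shown above. Some bias will remain where study-end scores are missing. Most cognitive tests in Table 2 are marked optional, so scores may be thinner for those than for the SDMT.
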